Mobile Health Technology: In the last decade, there has been an exponential growth in mobile health technologies (mHealth) with more than 400 brands and models of wearable activity monitors, including smartwatches, smartbands, rings and vests. Initially designed to track activity and heart rate, many devices now notify users of bradycardia, tachycardia and AF episodes. Most devices use very sensitive optical sensors and photoplethysmography (PPG) to analyse changes in skin colour, light intensity, and absorption to measure heart rate. In addition, advanced proprietary algorithms assess heart rate variability to diagnose AF. PPG technology has several inherent limitations that increase the number of false positive detections of AF, such as noise and artefact from changes in pressure, motion, skin tone and ambient light. More recently, an ECG sensor unit incorporated into smartwatches and rings generates a standard lead I (left arm to right arm vector) ECG which is transmitted to a smartphone app and can be exported in PDF format for further review by physicians. Wearable devices able to record 1-lead ECG can potentially identify other arrhythmias in addition to AF.

The European Society of Cardiology (ESC) recognises the pitfalls of wearable technologies in their recent guidance and recommends caution when interpreting published accuracy data from wearable devices. The guidelines state that AF diagnosis should not be based on PPG signals but can be diagnosed by physician interpretation of a single-lead ECG from a mobile or wearable device. Lastly, it highlights the need for robust validation studies prior to adopting wearable technology and 1-lead ECGs in routine clinical practice.

Undoubtedly, mHealth technology has many potential applications in healthcare, from monitoring cardiovascular risk factors and improving engagement and compliance to screening and monitoring of cardiac arrhythmias. However, the ubiquitous use of mHealth technologies— many without rigorous validation studies — will generate vast amounts of biometric data of uncertain quality and significance and will have several implications for both patients and physicians and for health economics. For patients, an ‘abnormal’ hearth rhythm detection may create significant anxiety and prompt them to take

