## 7. STUDY DESIGN

This study is a prospective, multicentre, observational study comparing rhythm and heart rate detection of two novel wearable devices — the Skylab CART-I ring and Apple Watch Series 6 — to a 12-lead ECG (gold-standard) for different cardiac rhythm disorders. We will recruit 500 participants attending Cardiology outpatient appointments, procedures or investigations (including the catheterisation laboratory) and inpatients in the cardiology and cardiothoracic wards in three hospitals across the UK. All patients will be due a 12-lead ECG as part of their standard of care.

If participants agree to take part in this study, the research team will provide them with instructions and will demonstrate how to use the wearable devices. Participants will then be asked to perform a simultaneous 30-seconds 12-lead ECG and 1-lead ECG for each wearable device (Skylab CART-I ring or Apple Watch). The order of recordings will be randomly assigned. If the first recording is uninterpretable due to artefact, a second recording will be allowed.

[figure not shown]
The SkyLabs CART-I Ring generates a 30-second 1-lead ECG by placing the participants finger on the rings' metal casing. Similarly, the Apple Watch 1-lead ECG requires the participant to place his/her finger on the metal crown. The 1-lead ECGs will be displayed and saved in the CART-I ring app and Apple Health app of a research iPhone SE, respectively. The smartphone apps will not contain any identifiable data and participants will only be identified by the time stamp of their recordings. The clocks of the Apple Watch, SkyLabs CART-I ring and ECG machine will be synchronised. The 12-lead ECG will also contain a time stamp and the study ID number (site code and participant number), it will then be recorded by using the iPhone SE camera and exported in PDF format for subsequent analysis. The 12-lead ECGs time stamp will also be documented in the CRF. The 12-lead ECGs will be added to the participants medical notes and available to the clinical team. The 1-lead ECGs from the wearable devices will only be available to the research team.

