This study does not involve any follow-up visits. All the 1-lead ECGs stored in the CART-I Ring app and Apple Health app will be exported in PDF format. All ECGs (12-lead ECGs and 1-lead ECGs from the wearable devices) will be analysed by two Cardiologists (based at Oxford University Hospital NHS Foundation Trust/OUHFT) blinded to patient's data. Any disagreement will be resolved by a third Cardiologist (CI of the study).

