## 10 STATISTICS AND ANALYSIS

Descriptive statistics are reported as count and percentage for categorical variables and mean and standard deviation for continuous variables.

Adjudication of all anonymised ECGs (12-lead ECGs, 1-lead ECGs from Apple Watch and SkyLabs CART-I ring) will be performed by two Cardiologists blinded to participants' data. Any disagreements will be decided by a third Cardiologist (CI of the study). Following adjudication, the sensitivity, specificity, positive negative predictive values will be calculated for different cardiac rhythm disorders. The level agreement between adjudicators will be calculated using the Cohen's kappa.

ECG waveform analysis and intervals (PR, QRS, QT and RR) will be measured by using callipers to the nearest 0.25 mm. The first three consecutive waveforms will be analysed in each ECG and the intervals averaged. In the 12-lead ECG, it will be to the physician's discretion which lead is chosen to measure the

intervals. To investigate the level of agreement, correlation coefficient and Band-Altman plots will be generated.

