Oxford CRM SkyLabs account). The CART-I smpl app will not have any identifiable patient information, only a time stamp. The 1-lead ECGs and PPGs recordings will be exported in PDF format for further analysis and stored in OUHFT computers. The study ID number will be added to the 12-lead ECG and a high-resolution photo will be taken with the research iPhone and uploaded to the iCloud. Adjudication of the 12-lead ECG will be performed in OUHFT computers.

The CRF contain will demographic data and past medical history which will be collected directly from the participants and their medical notes.

Data collected during this study may be used in anonymous form to support other research in the future.

Identifiable data will not be kept more than 5 years following the end of the study, unless participants would like to receive a summary of the study results in which case it will be kept for longer than 5 years.

Study data will be kept for a minimum of five years.

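### Section 10 does not require the same beats to be measured in the paired traces, so the interval limits of agreement can mix device error with avoidable beat-sampling scatter, mainly for RR in irregular rhythm

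*Combined protocol and SAP*

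**What the plan says.** Section 10 (Statistics and Analysis) has PR, QRS, QT and RR measured with callipers to 0.25 mm. The beats are chosen trace by trace: "The first three consecutive waveforms will be analysed in each ECG and the intervals averaged". On the reference lead it says: "In the 12-lead ECG, it will be to the physician's discretion which lead is chosen to measure the" intervals. Agreement is then examined with a correlation coefficient and Bland-Altman plots. No acceptable limit, expected standard deviation of differences or repeatability estimate is given.

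The wearables supply one lead. Section 5 says that the sensor "generates a standard lead I (left arm to right arm vector) ECG".

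The recordings are paired. Under Section 7, participants "perform a simultaneous 30-seconds 12-lead ECG and 1-lead ECG for each wearable device", and the clocks of the watch, the ring and the ECG machine are synchronised. The Wearable Devices section (8.9) repeats that watch and 12-lead recordings share the same 30 seconds, and describes the ring recording in the same way. Section 11.3 uses the time stamps to link a recording to its participant and site. No section uses them to line up beats.

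These measurements serve secondary objective 2 (Section 6), agreement of interval durations between each wearable and a 12-lead ECG.

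**The concern.** A Bland-Altman analysis attributes the scatter of paired differences to the measurement method. That reading is sound only if both methods measured the same thing. Here the design takes the trouble to record both traces at once, and the reading rule does not use it. Whichever three beats come first on each trace are averaged, and the two sets need not be the same.

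Section 8.9 describes starting the watch recording from its own app and crown, and the ring recording from the measure function of a phone app. It does not say how the 12-lead recording is started. Sharing a 30-second window does not guarantee a common first beat. In a regular rhythm this matters little. In AF, the arrhythmia at the centre of the study, successive RR intervals differ widely, and two different sets of three beats can have quite different means even if the device is perfect.

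The open lead choice is a second, smaller source. Intervals read in another lead need not equal those in lead I, and the reader may choose differently between participants, or between the two 12-leads of one participant.

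At stake is the interpretation of secondary objective 2. Wide limits could be read as poor interval measurement by the ring or watch when part of the width comes from the reading rule. The plan as written gives no means of separating the two.

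**Working it through.** The documents give no limits of agreement or standard deviation for the intervals, so there is no figure to reproduce. The check asks how wide the limits would be with no device error.

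**Inputs from the documents:** three beats averaged per trace; calliper resolution 0.25 mm; wearables record lead I; 12-lead lead free.

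**Assumptions:** beats independent within a recording; beat-to-beat standard deviation *s*; start offset of *k* beats between the traces; paper speed 25 mm/s, so 0.25 mm = 0.25/25 s = 10 ms.

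**Step 1: beat sampling.** If the traces start *k* beats apart (*k* up to 3), the two three-beat means share 3 − *k* beats, which cancel. The difference is the sum of *k* unshared beats in one trace minus the sum of *k* in the other, divided by 3. Its variance is 2*k s*²/9, and the 95% limits are ±1.96 × *s* × √(2*k*)/3. Beyond three beats nothing is shared and the value stays at *k* = 3.

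| RR, *s* (ms) | *k* = 0 | *k* = 1 | *k* = 2 | *k* ≥ 3 |
|---|---|---|---|---|
| 10 | 0 | ±9 | ±13 | ±16 |
| 30 | 0 | ±28 | ±39 | ±48 |
| 40 | 0 | ±37 | ±52 | ±64 |
| 150 (AF-like) | 0 | ±139 | ±196 | ±240 |

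For example, *s* = 150 and *k* = 1 gives 1.96 × 150 × √2/3 = 138.6 ms. A simulation of 200,000 draws at *s* = 150 gave 138, 195 and 239 ms for *k* = 1, 2, 3. With no shared beats, *s* from 105 ms (15% of 700) to 200 ms (25% of 800) gives ±168 to ±320 ms.

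**Step 2: calliper rounding, for scale.** One reading has variance 10²/12 = 8.33 ms². The difference of two three-reading means has 8.33 × 2/3 = 5.56 ms², or limits of ±4.6 ms.

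**Step 3: combine with device error.** Take an assumed device standard deviation of 10 ms and RR with *s* = 150.

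- Same beats: √(100 + 5.56) × 1.96 = ±20.1 ms.
- One-beat offset: √(5,000 + 100 + 5.56) × 1.96 = ±140.0 ms.
- Three or more: √(15,000 + 100 + 5.56) × 1.96 = ±240.9 ms.

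**Step 4: lead choice.** If reading another lead adds a difference with standard deviation *l*, it contributes ±1.96*l*: ±9.8, ±19.6 and ±39.2 ms for assumed values of 5, 10 and 20 ms. For QT with an assumed *s* of 5 ms, beat sampling at *k* = 3 adds at most 1.96 × 5 × √6/3 = ±8.0 ms. For QT, then, lead choice could matter more than beat choice. A systematic lead preference would shift the mean difference as well as widen the limits.

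**Step 5: sample size.** With 500 pairs, each limit is estimated to within about ±0.15 standard deviations of the differences. More participants would estimate the inflated limits more precisely, but would not narrow them.

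**The case against.** The strongest reply is that the recordings are simultaneous and the clocks synchronised, so the first three beats may coincide or overlap. This stands as a limit on the claim: a reader might infer that the beats are unmatched, but the documents do not say so. With coincident starts the beat-sampling term is zero. What remains is that matching is neither required nor checked, and that clock precision is not stated.

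Second, the large figures concern one interval in one type of rhythm. Eligibility is any adult with an indication for a 12-lead ECG, so the share of participants in AF is unknown. In regular rhythm the term is modest, and for QT with little beat-to-beat variation it is small. Heart rate also has its own comparison in secondary objective 3, based on mean rate from simultaneous acquisitions. All of this stands.

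Third, lead choice is partly a matter of what is being estimated. Objective 2 compares the wearables with a 12-lead ECG, not with lead I. If the question is whether a wearable interval matches what a physician would report from a 12-lead, the lead difference belongs in the answer. This also stands, so lead I need not become the main reference. It does not excuse leaving the chosen lead unrecorded.

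Fourth, the plan sets no acceptance limit, so wide limits would not trigger a formal failure. That lowers the stakes, but does not make the limits easier to interpret.

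**Conclusion.** The concern holds in a limited form. Section 10 permits different beats to be compared when the same beats are likely to be available in both traces, so the limits for secondary objective 2 can include avoidable scatter. Under independent beats, the contribution to RR limits at a standard deviation of 150 ms runs from zero (coincident starts) through about ±139 ms (one beat) to about ±240 ms (three or more). At 40 ms it does not exceed about ±64 ms. The standard deviations and offsets are assumptions. Lead choice may add to this, mainly for QT, by an amount the documents do not give.

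Two stronger readings are not supported. One is that the limits would reflect sampling and lead differences instead of device error. Device error always remains in them. With a device standard deviation of 20 ms, the non-device share of variance for RR at *s* = 150 and three or more beats offset is 15,005.56/15,405.56 = 97%. With the same beats it is 5.56/405.56 = 1%. The other is that photographing the 12-lead distorts the intervals materially. Section 11.3 does say that "a high-resolution photo will be taken with the research iPhone and uploaded to the iCloud", whereas the wearable traces are exported directly. But the documents give no scale error, and a measurement in millimetres can be read against the tracing's own grid.

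The primary objective, diagnostic accuracy of rhythm interpretation, is unaffected.

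**What to change.** Amend Section 10 in three respects.

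1. Replace the rule on the first three waveforms of each ECG with the first three consecutive beats legible in both simultaneous traces. Identify them by the RR pattern, with the synchronised time stamps as a guide only, because their precision is not stated. Report how many pairs could not be matched. Matching is hardest when the rhythm is very regular, but there a mismatch matters least (at most ±16 ms at a standard deviation of 10 ms).
2. Record which 12-lead lead was used for each measurement.
3. Add a comparison of wearable lead I with 12-lead lead I on the same beats. If the any-lead comparison stays as the main analysis, label this one a sensitivity analysis. The two together show how much of the disagreement comes from the lead.

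The cost is reading time. With 500 participants and two paired recordings each, there are 1,000 pairs to align, and up to 1,000 12-lead tracings to re-measure in lead I where the reader chose another lead. No new recordings, visits or participants are needed.

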## **11 DATA MANAGEMENT**

### **11.1 Source Data**

Source documents are where data are first recorded, and from which participants' CRF data are obtained. These include, but are not limited to, hospital records (from which medical history and previous and concurrent medication may be summarised into the CRF), clinical and office charts, laboratory and pharmacy records, diaries, microfiches, radiographs and correspondence.

CRF entries will be considered source data if the CRF is the site of the original recording (e.g. there is no other written or electronic record of data). All documents will be stored safely in confidential conditions. On all study-specific documents, other than the signed consent, the participant will be referred to by the study ID number, not by name.

### **11.2 Access to Data**

Direct access will be granted to authorised representatives from the Sponsor and host institution for monitoring and/or audit of the study to ensure compliance with regulations.

### **11.3 Data Recording and Record Keeping**

The participants will be identified by a unique study specific ID number (includes the site ID code and participant number) which will be assigned following consent. The study ID number (will be used in both hard-copies and electronic documents (PDF of 12-lead ECGs, excel spreadsheets for analysis and adjudication). The hard copies (CRF and consent forms) of data will be securely kept in the Research Fellows' Office at each site. The key to the study ID number for each site will be maintained on a single document will be kept in a separate folder in the PI's office.

The participants name and any other identifying detail will NOT be included in any trial data electronic file (PDF of 12-lead ECGs, 1-lead ECGs, excel spreadsheets for adjudication and analysis).

Each individual site will have an Apple Watch and SkyLabs CART-I rings (five different sizes) which will be paired with a research iPhone SE. No identifiable data will be recorded in the iPhone SE. Apple Watch 1-lead ECGs are transmitted to the research iPhone health app with no patient identifiable information. The time stamp on each ECG will be documented on the CRF and used to identify study participants. All the data pertaining to the Apple Watch will be stored in the research iPhone SE and uploaded to the iCloud so that it can be assessed remotely for adjudication. All 3 research iPhones (one per site) will be registered to a research account ([[contact]](mailto:[contact])) and thus all uploads to the iCloud can be accessed centrally by the investigators in OUHFT. Individual upload can be identified by the serial number for the CART-I rings and by the name of the Apple Watch (different for each site) and thus if there are two recordings with the same time stamp we can easily identify the site and match it to the matching 12-lead ECG.

The SkyLabs CART-I ring data is recorded to its app (CART-I smpl) in the iPhone SE and to a password protected Oxford CRM Skylab online account (<https://www.CART-Icardiotracker.com>; see Appendix C) created for the purpose of this study ([[contact]](mailto:[contact])). Only the investigators will have access to the

Oxford CRM SkyLabs account). The CART-I smpl app will not have any identifiable patient information, only a time stamp. The 1-lead ECGs and PPGs recordings will be exported in PDF format for further analysis and stored in OUHFT computers. The study ID number will be added to the 12-lead ECG and a high-resolution photo will be taken with the research iPhone and uploaded to the iCloud. Adjudication of the 12-lead ECG will be performed in OUHFT computers.

The CRF contain will demographic data and past medical history which will be collected directly from the participants and their medical notes.

Data collected during this study may be used in anonymous form to support other research in the future.

Identifiable data will not be kept more than 5 years following the end of the study, unless participants would like to receive a summary of the study results in which case it will be kept for longer than 5 years.

Study data will be kept for a minimum of five years.

## **12 QUALITY ASSURANCE PROCEDURES**

The study may be monitored, or audited in accordance with the current approved protocol, GCP, relevant regulations and standard operating procedures.

### **12.1 Risk assessment**

Not applicable

### **12.2 Study monitoring**

Not applicable:

### **12.3 Study Committees**

This is a small, multicentre study using commonly available devices with minimal patient risk, no oversight committees are required.

## **13 PROTOCOL DEVIATIONS**

A study related deviation is a departure from the ethically approved study protocol or other study document or process (e.g. consent process or administration of study intervention) or from Good Clinical Practice (GCP) or any applicable regulatory requirements. Any deviations from the protocol will be documented in a protocol deviation form and filed in the study master file.

## **14 SERIOUS BREACHES**

A “serious breach” is a breach of the protocol or of the conditions or principles of Good Clinical Practice which is likely to affect to a significant degree –

- (a) the safety or physical or mental integrity of the trial subjects; or
- (b) the scientific value of the research.

In the event that a serious breach is suspected the Sponsor must be contacted within 1 working day. In collaboration with the C.I., the serious breach will be reviewed by the Sponsor and, if appropriate, the Sponsor will report it to the approving REC committee and the relevant NHS host organisation within seven calendar days.

## **15 ETHICAL AND REGULATORY CONSIDERATIONS**

### **15.1 Declaration of Helsinki**

The Investigator will ensure that this study is conducted in accordance with the principles of the Declaration of Helsinki.

### **15.2 Guidelines for Good Clinical Practice**

The Investigator will ensure that this study is conducted in accordance with relevant regulations and with Good Clinical Practice.

### **15.3 Approvals**

Following Sponsor approval, the protocol, informed consent form, participant information sheet will be submitted to an appropriate Research Ethics Committee (REC), and HRA (where required) and host institutions for written approval.

The Investigator will submit and, where necessary, obtain approval from the above parties for all substantial amendments to the original approved documents.

### **15.4 Reporting**

The CI shall submit once a year throughout the study, or on request, an Annual Progress report to the REC Committee, HRA (where required) host organisation, Sponsor and funder (where required). In addition, an End of Study notification and final report will be submitted to the same parties.

### **15.5 Other ethical issues**

In the event of a clinically relevant arrhythmia being detected by the ICM but not by the pacemaker, the research team will take steps to quickly inform the subject's clinical team so that if required, it can be promptly acted upon.

### **15.6 Participant Confidentiality**

The study will comply with the General Data Protection Regulation (GDPR) and Data Protection Act 2018, which require data to be de-identified as soon as it is practical to do so. The processing of the personal data of participants will be minimised by making use of a unique participant study number only on all study documents and any electronic documents, with the exception of the CRF. All documents will be

stored securely and only accessible by study staff and authorised personnel. The study staff will safeguard the privacy of participants' personal data.

No identifiable details will be published.

